### **5.2 Study Population**

#### Inclusion Criteria

- Adult subjects (male or female  $\geq 40$  years)
- Acute non-disabling ischemic stroke (NIHSS  $\leq 3$  at the time of randomization) that can be treated with study drug within 24 hours of symptoms onset. Symptom onset is defined by the “last seen normal” principle.
- TIA (Neurological deficit attributed to focal brain ischemia, with resolution of the

deficit within 24 hours of symptom onset), that can be treated with study drug within 24 hours of symptoms onset and with moderate-to-high risk of stroke recurrence (ABCD2 score  $\geq 4$  at the time of randomization). Symptom onset is defined by the “last see normal” principle.

- Informed consent signed

#### Exclusion Criteria

- Diagnosis of hemorrhage or other pathology, such as vascular malformation, tumor, abscess or other major non-ischemic brain disease (e.g., multiple sclerosis) on baseline head CT or MRI.
- Isolated or pure sensory symptoms (e.g., numbness), isolated visual changes, or isolated dizziness/vertigo without evidence of acute infarction on baseline head CT or MRI.
- Modified Rankin Scale Score  $> 2$  at randomization (pre-morbid historical assessment)
- NIH Stroke Score  $\geq 4$  at randomization
- Clear indication for anticoagulation (presumed cardiac source of embolus, e.g., atrial fibrillation, prosthetic cardiac valves known or suspected endocarditis).
- Contraindication to clopidogrel or ASA.
  - Known allergy
  - Severe renal or hepatic insufficiency
  - Severe cardiac failure, asthma
  - Hemostatic disorder or systemic bleeding
  - History of hemostatic disorder or systemic bleeding
  - History of thrombocytopenia or neutropenia
  - History of drug-induced hematologic or hepatic abnormalities
  - Low white blood cell ( $<2 \times 10^9/l$ ) or platelet count ( $<100 \times 10^9/l$ ).

- Use of thrombolysis within 24 hours prior to randomization
- History of intracranial hemorrhage.
- Anticipated requirement for long-term non-study antiplatelet drugs, or NSAIDs affecting platelet function.
- Current treatment (last dose given within 10 days before randomization) with heparin therapy or oral anti coagulation.
- Gastrointestinal bleed or major surgery within 3 months.
- Planned or likely revascularization (any angioplasty or vascular surgery) within the next 3 months (if clinically indicated, vascular imaging should be performed prior to randomization whenever possible)
- Scheduled for surgery or interventional treatment requiring study drug cessation.
- Qualifying TIA or minor stroke induced by angiography or surgery.
- Severe non-cardiovascular comorbidity with life expectancy < 3 months.
- Women of childbearing age not practicing reliable contraception who do not have a documented negative pregnancy test.
- Currently receiving an investigational drug or device.

## **6 TREATMENTS**

### **6.1 Study Drugs**

This randomized double-blind study is primarily designed to compare a clopidogrel/aspirin combination versus an aspirin alone regimen. The two types of study tablets (75 mg active clopidogrel and placebo) are indistinguishable, identical in size, shape, color, appearance, and taste.

Minor side effects are unusual with the medication, so it is not anticipated that either subjects or clinicians will be able to differentiate the placebo from the active drug. Standard laboratory

tests cannot detect the effects of clopidogrel.

Investigators will not have access to the randomization (treatment) code, except in exceptional circumstances, such as occurrence of a serious adverse event for which knowledge of the study medication would be considered essential for treating the subject.

## **6.2 Formulations**

- ✧ Clopidogrel 75 mg tablets
- ✧ Placebo tablets of Clopidogrel 75 mg
- ✧ ASA 75 mg tablets
- ✧ Placebo tablets of ASA 75 mg

## **6.3 Route of administration**

- ✧ Oral

## **6.4 Dose regimen**

### **Group 1:**

- ✧ Day 1\*: four tablets of clopidogrel 75 mg and open label ASA (75 mg -300 mg)
- ✧ From D2 to D21±2 days: one tablets of clopidogrel 75mg and one tablet of ASA 75 mg per day
- ✧ From D22±2 days visit to D90±7 days(does not exceed 75 days between D21±2 days visit to D90±7 days): one tablets of clopidogrel 75mg and one tablet of placebo ASA 75 mg per day

\*On Day1, patients will receive open label ASA (between 75-300 mg) with dose at the discretion of the investigator. This represents the total dose given on D1(between75-300 mg), including any ASA treatment taken by the patient, or given in the emergency unit on the same day.

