### **Group 2:**

- ✧ Day 1\*: four tablets of placebo clopidogrel 75 mg and open label ASA (75 mg -300 mg)

- ◇ From D2 to D21±2 days: one tablets of placebo clopidogrel 75mg and one tablet of ASA 75 mg per day
- ◇ From D22±2 days visit to D90±7 days(does not exceed 75 days between D22±2 days visit to D90±7 days): one tablets placebo of clopidogrel 75mg and one tablet of ASA 75 mg per day.

\*On Day1, patients will receive open label ASA (between 75-300 mg) with dose at the discretion of the investigator. This represents the total dose given on D1 (between 75-300 mg), including any ASA treatment taken by the patient, or given in the emergency unit on the same day.

Study drug will be started **as soon as possible** after randomization (within one hour).

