**Patient box including box 1 and box 2**

Box 1 composed of two wallets: the first one is non-open-label clopidogrel or placebo clopidogrel (C1) containing 75mg \* 7 pills \* 4 pieces for period from Day 1 to Day 21 ± 2. The other one is non-open-label ASA (A1) containing 25mg \* 30 pills \* 2 piece + 6 pills for period from Day 2 to Day 21 ± 2.

Box 2 composed of two wallets for period from Day 21± 2 to Day 90± 7: the first one is non-open-label clopidogrel or placebo clopidogrel (C2) containing 75mg \* 7 pills \* 11 pieces. The other one is non-open-label ASA or placebo ASA (A2) containing 25mg \* 30 pills \* 8 pieces.

The content of the labeling will be in accordance with the local regulatory specifications and requirements.

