#### **7.4.3 Treatment Accountability and Compliance**

Compliance will be assessed by counting returned tablets at each visit.

The investigator (or delegates) will complete the appropriate page of the CRF or study drug inventory log form.

The date of study drug interruption must also be recorded.

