### **7.6 Blinding System and Emergency Unblinding Procedure**

#### **7.6.1 Description of blinding methods**

This randomized double-blind study is primarily designed to compare a clopidogrel /ASA combination followed by clopidogrel alone regimen versus an ASA alone regimen.

The two types of clopidogrel tablets developed (75 mg active clopidogrel and placebo clopidogrel) are indistinguishable (identical in size, shape, color, appearance).

The two types of ASA tablets developed (75 mg active ASA and placebo ASA) are indistinguishable (identical in size, shape, color, appearance).

No locally- used biological test that could potentially unblind the treatment is planned in this study.

Investigators will not have access to the randomization (treatment) code, except in exceptional circumstances, such as occurrence of a serious adverse event for which knowledge of the study medication would be considered essential for treating the subject.

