### **9.3 Three month Visit = D 90±7**

**Note: Number of days between D21±2 and D 90±7 visits may not exceed 75 days.**

During this visit:

- ✓ If the patient will be diagnosed by sICAD, MRI+MRA (MRI including T1 + T2 + DWI + FLAIR + T2\*) sequences will be strongly encouraged to perform. Images will be transferred to the core imaging evaluation lab.
- ✓ A neurological evaluation will be performed (Modified Rankin Scale and NIHSS)
- ✓ Quality of life scale (EQ-5D) will be performed in a quiet room (Appendix 4)
- ✓ A physical examination will be performed, including vital signs (supine systolic and diastolic blood pressure, heart rate)
- ✓ Information will be collected on concomitant medications and adverse events since the last visit
- ✓ The treatment box from completed study period with unused study medication will be collected for drug accountability and assessment of treatment compliance

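### The dose regimen calls for one 75 mg aspirin tablet a day, but the kit supplies 25 mg tablets in numbers that fit three a day

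*Supplement*

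**What the plan says.** The final English protocol describes the blinded aspirin in two ways.

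- **Section 6.2 (Formulations)** lists "ASA 75 mg tablets" and a matching placebo.
- **Section 6.4 (Dose regimen)** gives Group 1, from Day 2 to Day 21 ± 2, "one tablets of clopidogrel 75mg and one tablet of ASA 75 mg per day". Afterwards the aspirin tablet becomes one placebo tablet a day. Group 2 takes one 75 mg aspirin tablet a day throughout; its later period reads "one tablets placebo of clopidogrel 75mg and one tablet of ASA 75 mg per day".
- **Section 7.6.1 (Description of blinding methods)** states: "The two types of ASA tablets developed (75 mg active ASA and placebo ASA) are indistinguishable". It gives a strength but no daily count.
- **Section 7.2 (Packaging and Labeling)** describes the kit. For Box 1: "The other one is non-open-label ASA (A1) containing 25mg", as two strips of 30 plus 6. For Box 2: "The other one is non-open-label ASA or placebo ASA (A2) containing 25mg", as eight strips of 30.

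The final Chinese protocol also gives 75 mg per aspirin tablet in 6.2 and 7.6.1 and packs 25 mg tablets in 7.2. Its 6.4 gives the dose as 75 mg/day with no tablet count.

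On accountability, protocol 7.4.3 says: "Compliance will be assessed by counting returned tablets at each visit". The SAP (Treatment Compliance) divides doses taken by doses expected and sets the expected number to one per treatment day. Protocol 3.2.2 uses 80% of expected doses as the per-protocol threshold.

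**The concern.** Tablet strength and tablets per day are figures that sites act on, and here the regimen and the kit cannot both be right. The box contains no 75 mg aspirin tablet, so 6.4 cannot be carried out as written.

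Two things are at stake. The first is dosing at about 100 sites, with patients taking the drug home. A site that kept the tablet count and overlooked the strength would give 25 mg/day. Up to Day 21 this would reduce aspirin in both arms. After that, only the control arm's aspirin is active, so the shortfall would weaken the comparator alone.

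The second is compliance. It rests on returned tablets, and no section says how many aspirin tablets make one dose.

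**Working it through.** **Inputs**

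- Box 1 (7.2): aspirin 2 × 30 + 6 = 66 tablets of 25 mg; clopidogrel or its placebo 4 × 7 = 28 tablets of 75 mg, of which 4 are the Day 1 load (6.4).
- Box 2 (7.2): aspirin or placebo aspirin 8 × 30 = 240 tablets of 25 mg; clopidogrel or its placebo 11 × 7 = 77 tablets.
- Longest Box 1 aspirin period: Day 2 to Day 23, which is 23 − 2 + 1 = 22 days.
- Longest Box 2 period: 75 days. Section 9.3 notes that the interval between the two "visits may not exceed 75 days".

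**Days covered = tablets ÷ tablets per day**

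| Item | At one a day | At three a day | Longest need |
|---|---|---|---|
| Aspirin, Box 1 | 66 days | 22 days | 22 days |
| Aspirin, Box 2 | 240 days | 80 days | 75 days |
| Clopidogrel, Box 1 | 28 − 4 = 24 days | – | 22 days |
| Clopidogrel, Box 2 | 77 days | – | 75 days |

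In milligrams, Box 1 holds 66 × 25 = 1,650 mg = 22 × 75 mg, and Box 2 holds 240 × 25 = 6,000 mg = 80 × 75 mg. The clopidogrel counts fit one tablet a day with a small margin. The aspirin counts fit three a day, with Box 1 matching the longest window exactly.

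**Likely origin.** Protocol version 1.0 packed 36 aspirin tablets of 75 mg in Box 1 for Day 2 to Day 30 ± 7. The longest window was 37 − 2 + 1 = 36 days, an exact fit at one a day. The 75 mg wording in 6.2, 6.4 and 7.6.1 matches that kit and appears to have been kept when the packaging changed.

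**Dose under a literal tablet count.** One supplied tablet is 25/75 = 33% of the dose. Over Day 2 to Day 21 (20 days), that is 20 × 25 = 500 mg instead of 20 × 75 = 1,500 mg.

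**Compliance at a Day 21 visit, aspirin, over the same 20 days**

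| Patient takes | Tablets taken | Returned of 66 | If one tablet = one dose | If three tablets = one dose |
|---|---|---|---|---|
| Three a day | 60 | 6 | 60/20 = 300% | 20/20 = 100% |
| One a day | 20 | 46 | 20/20 = 100% | (20/3)/20 = 33% |

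Under the one-tablet wording of 6.4, the patient on a third of the dose counts as fully compliant.

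**The case against.** The strongest reply is that the dose is never in doubt. The synopsis, the objectives, the regimen and the SAP all give 75 mg/day, and 6.4 puts the strength in the same phrase as the count, so a site would have to ignore it to give 25 mg. Sites already make up aspirin doses from small tablets, because the public box supplies Day 1 aspirin as 50 mg and 25 mg tablets. The sites are in China, and the Chinese 6.4 carries no tablet count. Training, the Manual of Procedures and the labels may all state three tablets, and none of them is shown. The SAP counts doses rather than tablets, its own per-protocol rule is phrased in days off drug, and the primary Cox analysis does not use compliance.

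Most of this stands, and it limits the consequence: under-dosing is a possibility, not something the documents show, and the primary result is not threatened. It is also true that only 6.4 gives the daily count, and that three a day is inferred from the pack sizes rather than written anywhere. None of it reconciles the text. The regimen names a tablet that the kit does not contain, the Chinese protocol has the same conflict over strength, and a reader should not have to work out the tablet count by dividing pack sizes.

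**Conclusion.** The point holds. Within the current protocol, the aspirin tablet strength in 6.2, 6.4 and 7.6.1 and the daily count in 6.4 contradict the supplied kit. The pack counts show that the kit was built for three 25 mg tablets a day. This conclusion rests on the 7.2 counts being correct; the Chinese 7.2 gives the same ones.

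Followed literally on tablet count, the text gives a third of the intended dose. It also leaves open whether 6 or 46 returned aspirin tablets at Day 21 means full compliance. The intended dose of 75 mg/day, the sample size and the primary intention-to-treat analysis are unaffected. If three tablets are read as one dose, the SAP formula works as intended. The correction should be made because these are operative figures, even though no harm to the trial's estimates has been shown.

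**What to change.** - **6.2 and 7.6.1, English and Chinese:** give the blinded aspirin as 25 mg tablets with matching placebo tablets.
- **6.4, English:** from Day 2 onward, in both groups, specify three 25 mg aspirin (or placebo aspirin) tablets, 75 mg in total, once daily.
- **7.4.3, English and Chinese:** state that three aspirin tablets count as one dose when returned tablets are converted to compliance.

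The cost is wording only. Dose, kit contents, sample size and analysis model stay as they are.

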### **Group 2:**

- ✧ Day 1\*: four tablets of placebo clopidogrel 75 mg and open label ASA (75 mg -300 mg)

- ◇ From D2 to D21±2 days: one tablets of placebo clopidogrel 75mg and one tablet of ASA 75 mg per day
- ◇ From D22±2 days visit to D90±7 days(does not exceed 75 days between D22±2 days visit to D90±7 days): one tablets placebo of clopidogrel 75mg and one tablet of ASA 75 mg per day.

\*On Day1, patients will receive open label ASA (between 75-300 mg) with dose at the discretion of the investigator. This represents the total dose given on D1 (between 75-300 mg), including any ASA treatment taken by the patient, or given in the emergency unit on the same day.

Study drug will be started **as soon as possible** after randomization (within one hour).

## 7 STUDY DRUG HANDLING

---

### **7.1 Supply and Storage**

Sanofi-Aventis will supply the blinded investigational products (study drug and placebo) used in the study. All investigational drug supplies in the study will be stored in a secure, safe place, under the responsibility of the Investigator or other authorized individual, and under the conditions described on the labeling.

### **7.2 Packaging and Labeling**

Each patient will be assigned a "patient kit" according to the randomization list.

According to the study periods and visits, each patient kit will consist of both the public box and the patient box that includes two boxes. Each box is composed of two parts as following:

#### **Public box including the open-label aspirin (A0)**

Two wallets of the packaging for 1st day: the first one is 50mg\* 12 pills \*15 pieces; the other one is 25mg \* 30 pills \* 1 piece. ASA in public box is available to 30 patients.

---

**Patient box including box 1 and box 2**

Box 1 composed of two wallets: the first one is non-open-label clopidogrel or placebo clopidogrel (C1) containing 75mg \* 7 pills \* 4 pieces for period from Day 1 to Day 21 ± 2. The other one is non-open-label ASA (A1) containing 25mg \* 30 pills \* 2 piece + 6 pills for period from Day 2 to Day 21 ± 2.

Box 2 composed of two wallets for period from Day 21± 2 to Day 90± 7: the first one is non-open-label clopidogrel or placebo clopidogrel (C2) containing 75mg \* 7 pills \* 11 pieces. The other one is non-open-label ASA or placebo ASA (A2) containing 25mg \* 30 pills \* 8 pieces.

The content of the labeling will be in accordance with the local regulatory specifications and requirements.

**7.3 Responsibilities**

The Investigator, the Hospital Pharmacist, or other personnel allowed to store and dispense Investigational Product will be responsible for ensuring that the Investigational Product used in the clinical trial is securely maintained as specified by the Sponsor and in accordance with the applicable regulatory requirements.

All Investigational Product shall be dispensed in accordance with the Investigator's prescription, and it is the Investigator's responsibility to ensure that an accurate record of Investigational Product issued and returned is maintained.

Any quality issue noticed with the receipt or use of an Investigational Product (deficient IP in condition, appearance, packaging documentation, labeling, expiry date, etc.) should be promptly reported to the Sponsor, who will initiate a complaint procedure.

Under no circumstances will the Investigator supply Investigational Product to a third party, allows the Investigational Product to be used other than as directed by this Clinical Trial Protocol, or dispose of Investigational Product in any other manner.

## **7.4 Concurrent Treatment**

### **7.4.1 Prohibited Concomitant Treatments**

Use of the following medications after randomization and during the study period represents a protocol violation. However, if there is a clinical need that justifies the added risk of these interventions in the setting of study drug use, they should be employed at the discretion of the treating physician

- ✧ Open-label ASA (with the exception of day 1, see Figure 1)
- ✧ NSAIDs, Cox1 and Cox2 inhibitors. If absolutely necessary, NSAIDs may be given for less than 5 days but not sooner than 8 days after randomization
- ✧ Open-label thienopyridines (ticlopidine, clopidogrel)
- ✧ Dipyridamole
- ✧ All heparins
- ✧ Oral anticoagulants
- ✧ GPIIb/IIIa receptor antagonists
- ✧ Thrombolytics
- ✧ Vascular intervention (surgery and / or angioplasty of any vessel). If intervention is absolutely necessary within the three months period after randomization, study drug will be stopped 5 days prior to the intervention. Study treatment will then be restarted unless the patient needs to take open label clopidogrel or aspirin. In this case, study drug will be restarted only when treatment with open label antiplatelet therapy has been stopped.

### **7.4.2 Permitted Concurrent Treatments**

Any drugs other than those listed above are permitted (including anti-hypertensive medications), if considered necessary for the patient, with a stable dose (when possible), at the discretion of the Investigator. Given uncertainty about an interaction between omeprazole and

other proton pump inhibitors and clopidogrel, those previously taking a proton-pump inhibitor will be evaluated for the appropriateness of other agents, such as H2 blockers. New prescriptions for proton-pump inhibitors will be avoided whenever an H2 blocker or other agent is an acceptable option. Similarly, other drugs that theoretically may affect clopidogrel metabolism will be avoided, with others substituted. This list includes: esomeprazole (Nexium), cimetidine (which is available by prescription Tagamet and OTC as Tagamet HB), fluconazole (Diflucan), ketoconazole (Nizoral), voriconazole (VFEND), etravirine (Intelence), felbamate (Felbatol), fluoxetine (Prozac, Serafem, Symbyax), and fluvoxamine (Luvox).

Any treatment which is ongoing before randomization and/or prescribed or changed during the study must be recorded in the CRF.

#### **7.4.3 Treatment Accountability and Compliance**

Compliance will be assessed by counting returned tablets at each visit.

The investigator (or delegates) will complete the appropriate page of the CRF or study drug inventory log form.

The date of study drug interruption must also be recorded.

#### **7.5 Treatment Discontinuation**

The investigational product (IP) should be continued whenever possible. If the IP is stopped, it should be determined if the discontinuation can be made temporarily; permanent IP discontinuation should be a last resort. Any IP discontinuation should be fully documented in the CRF. In any case, the patient should remain in the study as long as possible.

Pregnancy will lead to definitive treatment discontinuation in all cases.

##### **7.5.1 Temporary treatment discontinuation with investigational product(s)**

Re-initiation of treatment with the Investigational Product will be done under close and appropriate clinical/and or laboratory monitoring (see Appendix 5 Decision Charts) once the Investigator has considered according to his/her best medical judgment that the role of the

Investigational Product(s) in the occurrence of the event concerned was unlikely and there is no other contraindication to continuing in the study.

All temporary treatment discontinuation (< 10 days) and the date of treatment re-initiation should be recorded by the Investigator on the appropriate CRF pages when considered to be confirmed

### **7.5.2 Definition treatment discontinuation with investigational product(s)**

A patient should discontinue the study drug for any of the following reasons:

- ✓ Intercurrent condition that requires discontinuation of the study (e.g. lab abnormalities, Appendix 5).
- ✓ Positive serum pregnancy test or desire to become pregnant
- ✓ Contraception cessation

### **7.5.3 Handling of patients after definitive treatment discontinuation**

Patients will be followed according to the study procedures as specified in this protocol up to the scheduled date of study completion, or up to recovery or stabilization of an AE, whichever comes last

All withdrawals should be recorded by the Investigator on the appropriate CRF pages when considered to be confirmed

All patients who have discontinued the study drug prior to the last visit should have a complete end-of-study visit at three months.

For patients considered lost to follow-up, the CRF must be completed up to the last visit performed. The Investigator should make every effort to contact the patient and to identify the reason why he/she failed to attend the visit and to determine his/her health status

### **7.5.4 Consequence**

Patients who have been withdrawn from the study cannot be included again in the study. Their patient number and treatment must not be re-used.

The investigator will call the IVRS to notify the treatment discontinuation and/or the patient's withdrawal.

Randomized patients will not be replaced.

